Enrolled participants who complete the required baseline components (cognitive assessment, hypnotic and relaxation exercise, baseline data and demographic form, and pre-treatment assessment period) will be randomized in stratified blocks to ensure that participants with each sex/gender and pain type (neuropathic, non-neuropathic, mixed or undetermined) have an equal chance of being randomized to one of the 3 conditions. Stratifying in this manner will ensure the groups are balanced to reduce variation in outcome that is associated with each stratification variable.

Sub-Study:

Recruitment will follow the protocol of the main study. We propose to recruit up to ~~135~~ 180* 195** of the ~~343~~ 355** parent grant participants in order to ensure complete data from 117 participants, assuming a 15% drop-out rate. Based on our experience, we anticipate that at least 75% of the parent sample will elect to join the sleep study.

*Due to a higher attrition rate than anticipated, we have increased the enrollment number from 135 to 180 to ensure the 117 completers needed. A 13% attrition rate was determined based on the main study. The actual attrition rate for the sleep study is 27%.

** Enrollment number increased to allow for the recruitment of a full cohort in the final cohort of the study.

A. SPECIFIC AIMS

A1. Problem Statement

Main Study:

As many as 50% of male and 75% of female Veterans presenting to Primary Care report chronic pain¹⁻⁴, and reporting rates are even higher in specialty clinics.⁵⁻⁷ Among Veterans returning from Iraq and Afghanistan, 82% report chronic pain,⁸ and the prevalence of painful musculoskeletal, joint, and back problems tends to increase in the years following deployment.⁹ Prevalent co-morbidities among Veterans, such as substance use disorders, sleep dysregulation, mood disorders, and Post Traumatic Stress Disorder (PTSD) can amplify the experience of pain and complicate treatment.¹⁰⁻¹² In Veterans, the presence of co-morbid pain and anxiety is associated with increased service utilization,¹³ while co-morbid pain and substance use increases the risk of medication misuse.¹⁴ Pain is also associated with greater depression and anxiety,¹⁵ sleep dysregulation^{12, 16}, decreased quality of life,¹⁷ and lower self-reported health.¹⁸

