Routine communication and coordination between the investigators of the three study sites (UW, VAPSHCS, and WSU) will occur primarily through via joint teleconferenced executive meetings on an as-needed basis throughout the sub-study. Research staff from all three sites will also meet via telephone on a regular basis to address recruitment and enrollment and general workload strategies.

D4. Participant Recruitment and Feasibility

Veterans will be recruited from several clinics and service lines at VAPSHCS: the Rehabilitation Care Service (which includes the Polytrauma Network Site for the northwest four states, the Multiple Sclerosis Clinic/Center of Excellence, Prosthetic/Limb Loss Clinic, and Musculoskeletal Clinic), and the Spinal Cord Injury Service. Each of these clinics sees 200-500 new Veteran patients per year and carries an ongoing patient load of 200 – 400 patients. We will also recruit patients from Primary Care as needed, which carries an ongoing patient load of 19,000 patients per year. Last, Veterans may be referred to the study by clinicians in other service lines or from VA community-based outpatient clinics (CBOC) , but we will not actively recruit Veterans from other service lines.

The recruitment sources described above will provide participants who are representative of the general Veteran population with a history of chronic pain, and enhance the generalizability of the study results.

D5. Participants

Main Study:

We propose to enroll up to ~~343~~ 355* participants in order to ensure complete data from 240 randomized participants, assuming a very conservative 30% drop-out rate (the dropout rate in our other studies has averaged 12%). We will monitor the dropout rate on an ongoing basis, and modify the number of participants recruited as needed to ensure a final sample of N = 240 study completers.

*Enrollment number increased to allow for the recruitment of a full cohort in the final cohort of the study.

A completer is someone who is enrolled, randomized and participated in at least one data assessment point following randomization.

If someone is enrolled and not a completer, they would be defined as either 1.) Enrolled, not randomized or 2.) Enrolled, randomized, did not provide any data after randomization

For Open Label: A completer is someone who is enrolled, selects treatment and participates in the post-treatment assessment point.

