not testable, but we can look at the variables that were observed in groups with and without missing outcomes data. No association between observed variables and the group (missing vs. no missing) will be considered an indication that the data are missing at random. In addition, we will look at the reported reasons for missing values when available. If we can assume data are missing at random, we will use multiple imputation procedures. If there appear to be non-random missing outcomes data, we will use two methods designed to account for this: Heckman's selection models and pattern-mixture models, both of which model the joint distribution of the outcome and the missing mechanism. In the case of non-ignorable missing data, we will use both methods as a sensitivity analysis. If less than 5% of the data is missing and we can assume ignorable missing data, the following analysis will be performed.

Hypothesis 1 states that Veterans randomly assigned to receive eight group sessions of HYP or MM will report significantly greater pre- to post-treatment decreases in average pain than Veterans receiving eight sessions of ED. The response variable will be change in average pain intensity score from pre- to post-treatment (Pre-treatment score – Post-treatment score). This response variable will be analyzed using an analysis of covariance (ANCOVA) with treatment condition (HYP, MM, ED) as the explanatory variable and the baseline pain as a covariate.

Support for Hypothesis 1 would emerge if a significant treatment main effect is present after adjusting for the baseline covariate, and subsequent post-hoc analyses indicate larger baseline to post-treatment decreases in pain intensity in the HYP and MM conditions, relative to the ED condition. The overall significance level for the test of the null hypothesis that all three treatments have equal effect will be set to 0.05.

Although we anticipate that HYP and MM will have similar effects on the primary outcome variable, these analyses will also allow us to compare the relative effects of HYP and MM with each other, as part of the exploratory aims/analyses.

Pairwise comparisons of the treatment groups will be performed using Tukey method (see for example, Analysis of Messy Data Volume 1: Designed Experiments, Second Edition, by GA Milliken and DE Johnson. 2009, chapter 3).

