Additional covariate and mechanism variables will be captured to explain sleep findings more completely. Routine and “as required” (PRN) medications for each participant will be recorded on the 7-day sleep log to aid in understanding how sleep or pain medicines relate to sleep measurements. Sleep data will be analyzed for relationships with data already collected within the parent grant, including depression scores and self-report of new self-hypnosis and mindfulness meditation skills practiced. In addition to the mediators already examined within the parent grant, sleep self-efficacy will be explored using a 4-item Sleep Self-Efficacy and Control Scale.⁸⁹ These mediator variables will be related to the sleep outcomes (not the pain outcomes as those are already analyzed for covariates in the parent grant) by including them as covariates in mixed-effects ANOVA, controlling for condition and time point. These will be exploratory analyses where type II error is more problematic than type I error; therefore no type I error threshold correction is envisioned. Mediator analysis results will be explicitly reported as exploratory.

D6y. Missing Data

Analyses to identify potential patterns in missing outcome data will be conducted to determine if they are missing at random (“ignorable”). Missingness at random is not testable, but we can look at the variables that were observed in both, group with missing and without missing outcomes data. No association between observed variables and the group (missing vs. no missing) will be considered an indication that the data is missing at random. In addition, we will also look at the reported reasons for missing values (when available). If we can assume missing at random data, we will use multiple imputation procedures. Currently, two methods are used when the data is considered not missing at random: Heckman’s selection models and pattern-mixture models, both of which model the joint distribution of the outcome and the missing mechanism. In the case of non-ignorable missing data, we will use both methods as a sensitivity analysis. If less than 5% of the data is missing and we can assume ignorable missing data, the following analysis will be performed.

D6z. Power Analyses

We performed power analyses, reported below, to ensure that the study had more than adequate power to test the hypothesis related to the effects of the treatments on the primary outcome (average pain intensity).

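### The missing-data rule uses the pattern of missing completely at random as its sign of missing at random, and so steers ordinary dropout away from multiple imputation into a branch with no primary estimate

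*Combined protocol and SAP*

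**What the plan says.** Section D6x (Statistical Analyses, Main Study) commits to intent-to-treat for Aim 1. Under Missing Data it accepts that MAR cannot be tested, and then gives a working sign for it: "No association between observed variables and the group (missing vs. no missing) will be considered an indication that the data are missing at random". It adds that reported reasons for missing values will be looked at where available. Three branches follow.

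- MAR assumed: "If we can assume data are missing at random, we will use multiple imputation procedures".
- Missingness appears non-random: Heckman selection models and pattern-mixture models, with the statement "In the case of non-ignorable missing data, we will use both methods as a sensitivity analysis".
- Little missing: "If less than 5% of the data is missing and we can assume ignorable missing data, the following analysis will be performed". The text after this sentence is the ANCOVA of change in pain with baseline pain as covariate, which is the test of Hypothesis 1.

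Section D6y gives nearly the same text, including "No association between observed variables and the group (missing vs. no missing) will be considered an indication that the data is missing at random". It too ends by announcing a following analysis, but what follows is D6z, the power section.

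**The concern.** The sign chosen for MAR is the pattern expected under MCAR. Under MAR, missingness may depend on anything observed, such as arm, baseline pain or the pain ratings after sessions 2, 4 and 6. An association with observed variables is therefore no evidence against MAR. It is the information that imputation should use.

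This check is the only data criterion offered for assuming MAR, and assuming MAR is the only route to multiple imputation. The check has no test, threshold or variable list. If dropout is related to baseline pain, which is common and benign, the rule points towards models that are run only as sensitivity analyses. Nothing in that branch is named as the test of Hypothesis 1, so the deciding result could be picked after the data are seen.

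The check also fails in the other direction. Dropout driven by an unobserved part of the outcome shows no association either, and would pass as MAR.

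**Working it through.** **Inputs from the documents.** Target of 240 completers, 80 per arm (Précis; D5; D6z). No missing rate is given for post-treatment pain among those randomised. The nearest figures are in D5, "the dropout rate in our other studies has averaged 12" (per cent), and in the Précis under Sample Size and Population, "A 13% attrition rate was determined based on the main study". D5 also plans for 30% dropout. A completer may still lack the primary outcome: "A completer is someone who is enrolled, randomized and participated in at least one data assessment point following randomization".

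**The plan's own figures.** Enrolment: 240 / (1 − 0.30) = 342.9, so 343, as planned before the increase to 355 for a full final cohort. Power: a one-way ANOVA with 80 per arm, SD 1, alpha 0.05 and the weakest stated scenario (decreases of 0.3, 0.8 and 0.6) gives 0.816, as claimed. Neither figure is in dispute.

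**Step 1: how often the 5% condition is met.** 5% of 240 is 12, so at most 11 may be missing. P(X ≤ 11), X ~ Binomial(240, p):

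| True missing rate p | Probability |
|---|---|
| 8% | 0.0267 |
| 10% | 0.00169 |
| 12% | 0.000065 |
| 13% | 0.000011 |

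At these rates the branch that introduces the ANCOVA would almost never apply.

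**Step 2: how often benign MAR dropout fails the check.** Assumptions: three arms of 80; baseline ~ N(0,1); post-treatment pain = 0.6 × baseline − effect + error, total SD 1 within arm; effects of 0.5 and 0.3 SD; logit P(missing) = a + b × baseline, with a set to give the missing rate; check = t-test of baseline pain, missing against observed, at 0.05; 4,000 trials per setting. The log-odds b run from 0.2 to 0.5 per SD, odds ratios of exp(0.2) = 1.22 to exp(0.5) = 1.65. Share of trials showing an association:

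| Missing | b = 0.2 | 0.3 | 0.4 | 0.5 |
|---|---|---|---|---|
| 8% | 13% | 24% | 40% | 54% |
| 12% | 17% | 31% | 51% | 69% |
| 13% | 19% | 34% | 54% | 71% |
| 20% | 23% | 46% | 68% | 86% |

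With b = 0 (MCAR) the share is 4.5% to 5.6%. In every setting the baseline-adjusted ANCOVA on observed outcomes has bias between −0.004 and +0.004 SD (Monte Carlo SE 0.002).

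**Step 3: dropout that depends on earlier pain.** 12% missing, 2,000 trials, 20 imputations using arm, baseline and week-6 pain. Checking baseline and week-6 pain finds an association in 22% to 71% of trials under MAR (71% for log-odds 0.5 on week-6 pain alone) and in 8% under MCAR. Multiple imputation followed by ANCOVA has bias between −0.003 and +0.006 SD (Monte Carlo SE 0.003), and 95% interval coverage of 0.944 to 0.964.

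A harsher two-arm example has 29% missing, active-arm dropout depending on observed week-6 change, and a true difference of 0.50. Imputation gives 0.50 and complete-case ANCOVA gives 0.71. The check, here on week-6 change, shows an association in 82% of these trials, so it points away from imputation where imputation is needed most.

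**Step 4: errors in the other direction.** With 343 participants, 30% missing and dropout driven only by an unobserved residual (odds ratios 1.5 and 2.5 per SD), a 0.05 test on an observed variable shows an association in 5.6% and 4.7% of trials. Such dropout nearly always passes as MAR. Under MCAR, screening k independent variables at 0.05 gives at least one association with probability 1 − 0.95^k: 0.23 for k = 5 and 0.56 for k = 16.

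**The case against.** The routing is partly inferred. The plan calls absence of association an indication, never says that an association rules MAR out, admits that MAR is untestable, and also considers reported reasons. MCAR is a special case of MAR, so the stated direction is not false in itself. A statistician who saw dropout related to baseline pain could assume ignorability and impute without breaching the text. The criterion for supporting Hypothesis 1 (treatment effect adjusted for baseline, at 0.05, with Tukey comparisons) carries no missing-data condition of its own, so ANCOVA on imputed data is probably meant. Failing the 5% condition under MAR leads to imputation, which is the method recommended here.

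On the numbers, 240 is the completer target rather than the randomised population, and 12% and 13% are attrition figures rather than missing rates for post-treatment pain. The association rates describe an assumed t-test. No Heckman or pattern-mixture model was fitted, so no bias is shown for that branch. The complete-case figure of 0.71 belongs to an analysis that the plan does not prescribe at 29% missing.

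These limits on the numbers stand. The main point survives them: a check on observed variables has no purpose unless its result changes the analysis, and the only alternative given is the non-random branch. No decision rule attaches to the reported reasons, so the discretion they allow makes the choice more dependent on the data. The probable intention to run ANCOVA on imputed data is unwritten, and no comparable reading supplies a primary estimate in the non-random branch.

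**Conclusion.** The rule is wrong as written, and it governs the test of the primary hypothesis. That conclusion rests on the definitions of MAR and MCAR and on the text of D6x and D6y, not on the simulations. The simulations indicate size only: under the assumed 0.05 test on baseline pain, 13% to 86% of trials with benign MAR dropout would fail the plan's sign of MAR, across 8% to 20% missing and log-odds of 0.2 to 0.5. The ANCOVA remains unbiased in all of those settings. The less-than-5% branch is very unlikely to apply at missing rates of 8% or more. The missing rates and log-odds are assumptions, because the documents give none for post-treatment pain. The wording should be corrected before the primary outcome is analysed.

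**What to change.** In both D6x and D6y, remove the association check and the 5% condition as deciders of the primary method. State one primary analysis for all randomised participants at any missing rate: multiple imputation under MAR, then the stated ANCOVA, with the overall test and Tukey comparisons combined across imputations by a named method.

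List the imputation variables: arm, baseline pain, pain after sessions 2, 4 and 6, and the stratification factors (sex/gender and pain type). All are already collected (D6k, D6l). Use the comparison of missing and observed groups only to choose further imputation predictors.

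Always run the pattern-mixture analysis, and the selection model if wanted, as sensitivity analyses whatever that comparison shows. Delete the dangling reference at the end of D6y, or replace D6y with a pointer to D6x.

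The cost is wording in two places and a little programming. No new data are needed, and the sample size does not change.

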Table 1. Study Design: Main Phase

Step	Data Collected	How Often/When
Cognitive Assessment	Cognitive functioning	Once following consent, before treatment begins
Relaxation and Hypnotic Exercise	Hypnotic responsivity	Once following consent, before treatment begins
Baseline Data and Demographic Form	Demographic and general health information, pain type	Once following consent, before treatment begins
Pre-Treatment Telephone Assessments	average pain intensity (primary outcome), worst pain intensity, depression, anxiety, sleep disturbance, pain interference, global health, medication use, post-traumatic stress, thoughts about pain, mindfulness, treatment motivation and expectancy, cognition	Once following consent, before treatment begins
Pre-Treatment EEG Brain Activity	Delta, theta, alpha, beta, and gamma power	Once following consent, before treatment begins

Randomization	No data collected	Once following completion of all baseline study procedures
Treatment	Homework completed between sessions, pain and comfort levels pre- and post-session, participant engagement as per clinician	Eight sessions avg. once per week
During Treatment Assessments	Average pain intensity (primary outcome), depression, anxiety, sleep disturbance, pain interference, global health, medication use, post-traumatic stress, thoughts about pain, mindfulness, group climate, therapeutic alliance,	After sessions 2, 4 and 6
Post-Treatment Telephone Assessment	average pain intensity (primary outcome), depression, anxiety, sleep disturbance, pain interference, global health, medication use, post-traumatic stress, thoughts about pain, mindfulness, global satisfaction, therapeutic alliance, treatment satisfaction, treatment modality and feedback, cognition	Once following end of treatment
Post-Treatment EEG Activity Assessment	Delta, theta, alpha, beta, and gamma power	Once following end of treatment
3 Month Telephone Assessments	Average pain intensity (primary outcome), depression, anxiety, sleep disturbance, pain interference, global health, medication use, post-traumatic stress, thoughts about pain, mindfulness and global satisfaction, cognition	Three months following end of treatment
6 Month Telephone Assessments	Average pain intensity (primary outcome), depression, anxiety, sleep disturbance, pain interference, global health, medication use, post-traumatic stress, thoughts about pain, mindfulness	Six months following end of treatment

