The assessment period described above will be completed prior to initiating treatment, and then after completion of treatment sessions #2, 4 and 6 and 8 (i.e. post-treatment), and 3 and 6 months following the end of treatment for a total of seven times. These assessment periods that occur following the start of treatment will also include questions about group climate, therapeutic alliance with the group clinician, treatment satisfaction, feedback about the treatment modality, and overall improvement since the participant began the pain program. The open-ended questions regarding treatment satisfaction and feedback on treatment modality will be collected by an unblinded staff member. Group Comfort Questions will be administered by an unblinded staff member at any time after session 8 (final group session). This assessment is optional. The window is from post-treatment until the participant is disenrolled.

Staff will send via USPS mail a reminder letter prior to the 3- and 6-month assessment periods.

As mentioned above, during the consent process research staff will provide participants with a response key to help answer questions asked during the telephone assessment periods. Participants may request research staff send another response key to them if they lose the key during study participation. Research staff will send the response key along with a cover letter via USPS mail.

Participants will be compensated \$25 for the completion of each assessment period via a check written from the Seattle Institute for Biomedical and Clinical Research (SIBCR). The check will be sent via USPS mail and accompanied by a payment cover letter.

The pre-treatment assessment period may take place up to four weeks prior to the start of the treatment groups for that particular cohort.

D6I. Randomization

Enrolled participants who complete the required baseline components (cognitive assessment, hypnotic and relaxation exercise, baseline data form, and pre-treatment assessment period) will be randomized in stratified blocks to ensure that participants with each sex/gender and pain type (neuropathic, non-neuropathic, mixed or undetermined) have an equal chance of being randomized to one of the 3 conditions. Stratification will assure that the treatment groups are balanced regarding each stratification variable, so that the estimated effect of the treatment is not biased due to differences in distribution of sex/gender or type of pain.

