Addressing Aim 2 by testing Hypothesis 2. Hypothesis 2 states that baseline EEG activity will predict differential response to HYP and MM, such that those participants who have higher baseline levels of global theta, and lower baseline levels of left frontal gamma will respond to HYP, while participants with lower baseline levels of global alpha will respond to MM. We will test for this moderator using a linear regression analysis, with pre- to post-treatment change in pain intensity as the response (criterion) variable. Treatment Condition, absolute power of baseline theta, alpha, and (left frontal) gamma, and terms representing the interaction between treatment condition and each EEG bandwidth will be the explanatory variables. Significant Treatment Condition X Theta, Alpha, and Gamma interactions, with higher coefficients for baseline theta and lower coefficients for baseline gamma in the HYP group, and lower coefficient for baseline alpha in the MM group would support Hypothesis 2.

Additional exploratory analyses. In addition to testing the two study hypotheses, we propose a series of exploratory analyses (explained below) to take full advantage of the data collected to better understand the effects and potential mechanisms of HYP and MM. However, because these analyses are exploratory, we will report them as such. Any statistically

significant findings will be viewed as providing support for further, more definitive, testing in the future.

Effects of HYP and MM on secondary outcomes. To examine the potential effects of HYP and MM, relative to ED, on co-morbid conditions, we will repeat the ANCOVA analyses planned to test Hypothesis 1 for the secondary outcome variables (assessing pre- to post-treatment decreases in depression, anxiety, sleep disturbance, pain interference, PTSD symptoms) as the response variables, controlling for the respective baseline measures of these secondary outcomes. The response variable will be change in each outcome measure score from pre- to post-treatment (Pre-treatment score – Post-treatment score). This response variable will be analyzed using an analysis of covariance (ANCOVA) with treatment condition (HYP, MM, ED) as the explanatory variable and the corresponding baseline value for each secondary outcome measure as a covariate.

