Perceived global improvement is a secondary outcome measure but unlike the other secondary outcome measures it was not measured at baseline, hence a slightly different approach will be used for this secondary outcome measure. Instead of a change score, we will simply use ANOVA to compare perceived global improvement with treatment condition as the independent variable.

To assess the effect of each treatment on post-treatment ratings of global satisfaction (which has only 5 categories), we will use an ordinal polytomous logistic regression. Because we anticipate that *both* HYP and MM will have significant beneficial effects on outcomes, we do not anticipate large differences between these two interventions in the outcome measures. However, we think that it would be important to estimate differences in outcome between the two active treatments for descriptive purposes. To do so, we will perform pairwise post-hoc tests to compare the means of the three groups.

We will report both the p-value and effect sizes for the tests between the two conditions (HYP and MM) on outcomes. While the study was not powered to simultaneously test for the primary and secondary outcomes, it is reasonable to assume that the sample size of 80 participants per condition (determined to adequately power the primary hypotheses) will allow for reliable estimates of the effect sizes for secondary outcomes as well.

Longer-term effects of HYP and MM, relative to ED.

As part of our exploratory aims, we plan to assess the extent to which change in pain intensity, the primary outcome, is maintained at 3 and 6 months post-treatment, and to see if longer term changes in pain intensity differ between HYP and MM compared to ED. To assess this, we propose to use a Generalized Estimating Equations (GEE) approach, which accounts for the correlated nature of the data due to multiple observations of the same person over time. Response variables over time will be the change from pre-treatment to post-treatment, and pre-treatment to 3- and 6- months follow-ups, with intervention group and follow-up time as the main factors of interest (including a Group X Time interaction), and the pre-treatment value as the covariate. For the correlation matrix, we will assume an unstructured format, since there was no a priori reason to use a more structured matrix format. We will repeat these analyses for the secondary outcome measures mentioned above.

Mediation analyses.

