As a secondary sleep outcome, for this aim we will add the PROMIS Sleep Disturbance Short Form, which is already being administered as a self-report measure of sleep quality within the parent project. This will allow us to evaluate the level of congruence between the parent grant and the subsample studied in the supplement.

For the statistical analyses in support of aim 2, we will determine whether changes in self-reported sleep quality and in actigraphic sleep duration in the hypnosis and mindfulness meditation treatment groups and the control group *precede* changes in pain, or vice versa, from pre-treatment to mid-treatment to immediate post-treatment to 3-month follow-up. Specifically, we will evaluate the association between early treatment changes in self-reported sleep quality (from pre-treatment to mid-treatment) and late treatment changes in pain (from mid-treatment to post-treatment), and vice versa.

We will also evaluate the association between treatment-related changes in objective sleep duration (from pre-treatment to post-treatment) and post-treatment changes in pain (from post-treatment to 3-month follow-up), and vice versa. *We hypothesize that changes in sleep quality and duration precede (and thus predict) subsequent changes in pain intensity.* Secondly, we will investigate whether associations are moderated by treatment group. *We hypothesize that larger lagged effects will occur for the two treatment conditions, relative to the control condition.* Our hypothesis testing for aim 2 will be based on cross-lagged regression analysis.^{103, 104}

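### Pain ratings after sessions 2, 4 and 6 enter no main-study efficacy model and are not required in the imputation, so dropout that follows early response differently by arm can bias the post-treatment contrast

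*Combined protocol and SAP*

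**What the plan says.** **Collection.** D6k schedules the pain assessment period "prior to initiating treatment, and then after completion of treatment sessions #2, 4 and 6 and 8", and again at 3 and 6 months, seven periods in all. Table 1 lists average pain, labelled as the primary outcome, in its during-treatment row ("After sessions 2, 4 and 6"), and Table 5 agrees. Under treatment discontinuation in D6n, people withdrawn from the classes are still invited to the 2-, 4- and 6-week assessments and to all later ones, expressly to serve the intent-to-treat analysis.

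**Use (D6x, main study).**
- Hypothesis 1: "The response variable will be change in average pain intensity score from pre- to post-treatment", analysed by ANCOVA with "treatment condition (HYP, MM, ED) as the explanatory variable and the baseline pain as a covariate".
- Aim 2: a regression "with pre- to post-treatment change in pain intensity as the response (criterion) variable".
- Longer-term effects, by GEE: "Response variables over time will be the change from pre-treatment to post-treatment, and pre-treatment to 3- and 6- months follow-ups".
- Mediation: the mediators are taken midway, but the pain outcome is again baseline to post-treatment.
- Only the sleep sub-study uses mid-treatment pain, through "late treatment changes in pain (from mid-treatment to post-treatment").

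**Missing data (D6x, repeated in D6y).** Missingness is compared with observed variables, and finding no association counts as evidence of missing at random. Multiple imputation follows in that case. If missingness looks non-random, Heckman selection and pattern-mixture models are used. The ANCOVA is introduced for the case of under 5% missing and ignorable. Neither section says which variables enter the check or the imputation model.

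**The concern.** For a person who stops answering before post-treatment, the latest interim rating is the best available guide to the missing value. Nothing in the main-study plan requires it to be used. Imputing from arm and baseline alone would comply with the text, and it would treat a leaver who was not improving at week 4 like one who was.

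The missing-at-random rule adds to the problem. Dropout driven by recorded week-4 pain is missing at random given that rating. The rule looks for no association with observed variables, which is in effect a check for missing completely at random. If interim pain is in the check, such dropout is labelled non-random and sent to Heckman and pattern-mixture models, away from the ratings that explain it. If interim pain is not in the check, the dropout can pass unnoticed and be imputed without those ratings.

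What is at stake is the size of the primary HYP-ED and MM-ED differences and, to a lesser degree, their precision.

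**Working it through.** **1. The plan's own figures.** D6z takes mean decreases of 0.3 (ED), 0.8 (HYP) and 0.6 (MM) as its least favourable case, with SD 1, alpha 0.05 and 80 per arm. One-way ANOVA power from the noncentral F is 0.816, so the stated 80% holds (78 per arm would do). Enrolment is 240/0.70 = 342.9, or 343, the figure in the timeline chart. The current 355 adds room for a full last cohort.

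**2. Which missing rate applies.** D5 divides enrolled non-completers into those never randomised and those randomised with no later data. Neither group has interim ratings, so the 30% does not describe the people at issue: randomised, rated at least once during treatment, and without a post-treatment score. The documents give no rate for them. I use 12%, the average dropout that D5 reports for the team's other studies, as an illustration.

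**3. Bias.** Assumptions not in the documents:
- HYP and ED only, with linear improvement to 0.8 and 0.3 (true difference 0.50) and change SD 1 at every visit.
- Exchangeable correlation rho between visits of 0.3, 0.5 or 0.7.
- Baseline unrelated to change, so baseline-only imputation equals complete case.
- Everyone seen to week 4, then dropout by a logistic function of week-4 change.
- 400,000 per arm (1,000,000 for the shared rule).

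| Dropout mechanism | Missing | Complete case or baseline-only imputation | Using weeks 2 and 4 |
|---|---|---|---|
| Non-response in HYP only, log-odds slope 1; rho 0.3, 0.5, 0.7 | 12% | 0.531, 0.553, 0.574 | 0.498-0.499 |
| Same, slope 2 | 12% | 0.550, 0.586, 0.613 | 0.497-0.502 |
| Slope 1 and equal rate in both arms | 12% | 0.500-0.502 | 0.499-0.503 |
| One shared rule, slope 1 | ED 11%, HYP 9% | 0.487-0.494 | not run |
| One shared rule, slope 1 | ED 35%, HYP 30% | 0.474-0.488 (complete case) | not run |

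The one-arm results can be checked by hand. Bias = rho x (mean week-4 change among stayers minus the arm's full mean). For slope 1, 0.031/0.3, 0.053/0.5 and 0.074/0.7 all give about 0.10 to 0.11. For slope 2, 0.050/0.3, 0.086/0.5 and 0.113/0.7 give about 0.16 to 0.17. So stayers in HYP look about 0.1 to 0.17 points better at week 4 than the whole arm, and the fraction rho of that carries to post-treatment. With the same selection in both arms the shift cancels.

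**4. Precision.** Assume correlations that decay with time: baseline to post-treatment 0.44-0.56, week 6 to post-treatment 0.65-0.80. Weeks 2 to 6 then explain about 30-50% of the post-treatment variance left after baseline (R2). Counting each missing person as worth R2 of an observed one, the gain is R2 x m/(1 - m):
- m = 0.12, R2 = 0.30: 0.30 x 0.12/0.88 = 4.1%.
- m = 0.12, R2 = 0.50: 0.50 x 0.12/0.88 = 6.8%.
- The stricter regression-estimator form, 1/(1 - R2 x m) - 1, gives 1/0.964 - 1 = 3.7% and 1/0.940 - 1 = 6.4%.
- Last seen at week 2, R2 = 0.07-0.10: 0.07 x 0.12/0.88 = 1.0% to 0.10 x 0.12/0.88 = 1.4%.

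**The case against.** The strongest reply is that the plan does not run an unprotected two-point analysis. It promises intent-to-treat, multiple imputation if data are judged missing at random, and Heckman and pattern-mixture models if not, and it ties the direct ANCOVA to under 5% missing. Interim pain is not excluded from any of these. Someone who misses post-treatment but answers at 3 or 6 months enters the GEE. Outcomes are collected by telephone, each assessment period is paid, a bonus rewards completing all seven, and leaving the class does not end assessment. ED is designed not to reduce pain, so a non-response rule common to both arms would remove more ED participants and bias the estimate slightly towards zero. Baseline-adjusted ANCOVA with good imputation draws on essentially the same information as a mixed model.

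Most of this stands, and it rules out three stronger readings that a reader might reach:
- *That anyone lost before post-treatment contributes only a baseline.* The imputation variables are unstated, so the documents do not settle this either way.
- *That the effect will be biased, or biased upwards.* Bias needs a mechanism that differs by arm, and the documents give no evidence on why participants leave.
- *That 30% loss makes the problem large.* Step 2 shows why that figure cannot be used here.

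The reply does not remove the gap. Interim pain is optional in the imputation, and the missing-at-random rule can steer the analysis away from it in just the case where it would help.

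**Conclusion.** The point holds as a weakness in specification with a clear better method. No main-study efficacy model of pain uses the session 2, 4 and 6 ratings, and no rule requires them in the imputation, although the protocol keeps collecting them from people withdrawn from treatment for the sake of the intent-to-treat analysis.

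If imputation rests on arm and baseline, or a complete-case ANCOVA is run, the HYP-ED contrast *can* be biased. At 12% missing with dropout tied to early non-response in one active arm only, 0.50 becomes 0.53 to 0.61, or 6 to 22% too large (0.03/0.50 to 0.11/0.50). It is unbiased with equal slope and rate in both arms, and 0.47 to 0.49 under a shared rule, the lower end only at 30 to 35% missing. These sizes depend on the assumed correlations, linear improvement and dropout after week 4. They illustrate what the wording permits and do not estimate bias in this trial. The precision gain is modest: about 4 to 7% at 12% missing if leavers were seen at week 6, and near 1% if last seen at week 2.

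The change is worth making because it costs almost nothing.

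**What to change.** Keep the post-treatment contrast, the three-arm omnibus test at 0.05 and the Tukey comparisons. Then write one of these into D6x:

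- **(a)** Estimate them from a repeated-measures mixed model of pain change at weeks 2, 4 and 6, post-treatment, 3 and 6 months, with arm, time, arm x time, baseline pain x time and unstructured covariance. The omnibus and Tukey tests are applied to the arm differences at post-treatment.
- **(b)** Keep the ANCOVA with multiple imputation run separately by arm, and require week 2, 4 and 6 pain in the imputation model, with 3- and 6-month pain where available.

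In D6x and D6y, change the missing-data rule: an association between missingness and observed interim pain should lead to conditioning on those ratings under missing at random. Keep the Heckman and pattern-mixture models as sensitivity analyses.

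Replacing the exploratory GEE is optional. No new data are needed and the estimand is unchanged. The cost is SAP wording and a slightly larger model to specify.
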